The baseline demographic data will be presented descriptively. Continuous data will be summarized as mean with standard deviation or median with interquartile range depending on the distribution of the data. Categorical data will be summarized using frequencies with percentage. Summary demographic statistics between patients with and without eye abnormalities will be compared using unpaired t-test (normal) and/or Mann-Whitney U test (skewed) for continuous data, and Chi-square test and/or Fisher's exact test (if any of the expected cell frequencies are <5) for categorical data. Normality assumption will be checked by using statistical test (e.g., Shapiro Wilk test) as well as graphical methods (e.g., histogram, q-q plot).

To assess our primary and secondary hypothesis, sensitivity and specificity of the red reflex test (RRT) will be determined along with their 95% confidence interval using contingency tables for both anterior and posterior segment pathology. Positive predictive value (PPV), negative predictive value (NPV), and area under ROC curve (AUC) will also be determined. We

will also compare sensitivity and specificity of RRT for both anterior and posterior pathology between with and without pharmacologic dilation using two-sided McNemar's test for correlated proportions.

All statistical tests will be two-sided and will be performed at the 5% level of significance unless otherwise stated. Stata 15.1 software will be used for all statistical analyses.

*Our sample size calculation is based on our primary hypothesis. Assuming a 75% prevalence of anterior or posterior segment pathology and a sensitivity of 90% in our sample, a total of **59** patients will be required to construct a two-sided 95% sensitivity confidence interval with a width of at most +/-10%. Under the same assumptions, the sample size needed for a two-sided 95% specificity confidence interval of +/-10% around 80% is **280**. We will take the larger one of these two, which is **280**. The power analysis was carried out using PASS 2019 software.*

Section 1: Key Roles

Principal Investigator
[name], Vice-Chair, Ophthalmology
Children's National Health System
[name]
[contact]
[contact]

Performance	Performance Site PI	Describe Activities Conducted at
--------------------	----------------------------	---

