8.5 Sample Size

*Our sample size calculation is based on our primary hypothesis. Assuming a 75% prevalence of anterior or posterior segment pathology and a sensitivity of 90% in our sample, a total of **59** patients will be required to construct a two-sided 95% sensitivity confidence interval with a width of at most +/-10%. Under the same assumptions, the sample size needed for a two-sided 95% specificity confidence interval of +/-10% around 80% is **280**. We will take the larger one of these two, which is **280**. The power analysis was carried out using PASS 2019 software.*

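### Section 8.5 states precision as plus or minus 10 points, but 59 and 280 come from a total exact-interval width of 20 points; at 280 the specificity interval runs 11.3 points below 80%

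*Combined protocol and SAP*

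**What the plan says.** Section 8.5 (Sample Size) starts from these assumptions: "Assuming a 75% prevalence of anterior or posterior segment pathology and a sensitivity of 90% in our sample". It then says that "a total of 59 patients will be required" "to construct a two-sided 95% sensitivity confidence interval with a width of at most +/-10"%. For specificity it gives a "two-sided 95% specificity confidence interval of +/-10% around 80% is 280", and concludes: "We will take the larger one of these two, which is 280". The Statistical Analysis part of the Protocol Summary carries the same text.

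The only statement of method is that "The power analysis was carried out using PASS 2019 software". Neither 8.5 nor 8.4 (Description of Statistical Methods) names the type of confidence interval. Section 8.5 also does not say whether the 10 points limit each side of the interval or are half of a total width.

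**The concern.** Plus or minus 10 points around 80% would ordinarily be read as 70% to 90%. If the two totals came from an asymmetric interval and were solved on its total width, the lower side is longer than 10 points and the plan describes its precision too favourably.

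The lower side is the one a reader will look at. The Protocol Summary hypothesises that the test is sufficient for anterior segment disease, and the lower confidence limit tells a reader how poor the accuracy could still be. What is at stake is an accurate statement of expected precision, not whether the study can answer its question.

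**Working it through.** **Inputs.** From 8.5: two-sided 95% confidence, prevalence 0.75 (so 0.25 without pathology), sensitivity 0.90, specificity 0.80, totals 59 and 280, with 280 adopted. From 5.1: 200 participants including 100 controls, hence 200 − 100 = 100 cases. From the Protocol Summary: cases are split into an anterior and a posterior group. From 3.1: accuracy for each segment is a primary outcome.

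**Formula.** Exact limits for x = n·p positives out of n: lower = Beta quantile at 0.025 with parameters (x, n − x + 1); upper = Beta quantile at 0.975 with parameters (x + 1, n − x). The expected count n·p may be a non-integer (39.6 of 44). The lower arm is p − lower and the upper arm is upper − p.

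**Step 1: reproduce 59 and 280.** Take the smallest n with upper − lower ≤ 0.20.
- Sensitivity, p = 0.90: width is 0.2007 at n = 43 and 0.1982 at n = 44. Total = 44/0.75 = 58.7, rounded up to 59.
- Specificity, p = 0.80: width is 0.2003 at n = 69 and 0.1989 at n = 70. Total = 70/0.25 = 280.

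Both match exactly. The alternatives do not reproduce the pair:

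| Interval | Total for sensitivity | Total for specificity |
|---|---|---|
| Exact, total width ≤ 20 points | 59 | 280 |
| Wald | 47 | 248 |
| Wald, continuity-corrected | 60 | 288 |
| Wilson | 50 | 240 |
| Agresti-Coull | 55 | 248 |
| Jeffreys | 47 | 240 |

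**Step 2: the intervals these sizes give.**

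| Case | n | Exact 95% interval | Lower arm | Upper arm |
|---|---|---|---|---|
| Specificity 80%, N = 280 | 70 | 68.7% to 88.6% | 11.3 | 8.6 |
| Sensitivity 90%, N = 280 | 210 | 85.1% to 93.7% | 4.9 | 3.7 |
| Sensitivity 90%, N = 59 (not adopted) | 44 | 77.2% to 97.0% | 12.8 | 7.0 |
| Specificity 80%, section 5.1 | 100 | 70.8% to 87.3% | 9.2 | 7.3 |
| Sensitivity 90%, section 5.1, one segment (50 assumed) | 50 | 78.2% to 96.7% | 11.8 | 6.7 |

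**Step 3: does the specificity result depend on the exact method?** With 70 controls at 80%, the lower arm is 10.8 points by Wilson, 10.9 by Agresti-Coull and 10.5 by Jeffreys. Only Wald is inside, with a half-width of 1.96 × √(0.80 × 0.20/70) = 9.4 points, and Wald does not give 280.

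**Step 4: what a limit on each side would need.** An exact lower arm of at most 10 points needs about 65 cases at 90% (65/0.75 = 86.7, total 87) and about 87 controls at 80% (87/0.25 = 348; 86 controls and 344 in total if only whole counts are used). With 100 cases in two groups, both cannot reach 65, so at least one segment exceeds 10 points whatever the split.

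**The case against.** The strongest reply is that width in 8.5 means a total of 20 points written as a half-width. On that reading the target is met: the widths are 19.8 points at 59 and 19.9 at 280, averaging 9.9 on each side. This stands, and it is why the sample sizes themselves are not in error. It does not rescue the specificity sentence, where plus or minus 10 around 80% describes a symmetric range that the calculation behind 280 does not produce.

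A second reply is that the analysis interval is not named and Wald half-widths are within 10 points. That is true, and Clopper-Pearson is an inference from the match in step 1. But Wald cannot be the source of 59 and 280, and the other three methods tried also exceed 10 points on the lower side.

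A reader might infer more than the documents support:
- That the design can put the lower limit for sensitivity no higher than 77%. That interval belongs to 59, which 8.5 sets aside for 280. With 210 cases the lower limit is 85.1%, and with an assumed even split (105 per segment) it is 82.6%.
- That the plan promises a lower limit of 80%. No threshold for sufficient or poor accuracy, and no decision rule tied to a limit, appears in the Summary or in sections 3.1, 8.2 or 8.5.
- That the promised precision is simply not delivered. The total-width target behind both figures is met.

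**Conclusion.** The point holds as a wording fault of minor weight. The stated precision is slightly too favourable for the calculation that fixed the sample size. At the adopted 280, the excess is 11.3 − 10 = 1.3 points on the lower side of specificity, and there is none for pooled sensitivity. Under section 5.1 the excess moves to sensitivity by segment, 11.8 − 10 = 1.8 points at 50 cases each, while specificity comes inside.

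This rests on the exact method being the one used, on 8.5's anticipated values of 90% and 80%, and on patients as the unit, as in 8.5. Section 3.3 counts eyes, and eye-level counts would differ. The even split by segment is an assumption, but the miss in at least one segment under 5.1 is not. No planned conclusion changes.

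**What to change.** In 8.5 and the Protocol Summary, replace both plus-or-minus statements with a target of a total exact (Clopper-Pearson) 95% interval width of at most 20 points. Name the same interval method in 8.4. Print the expected limits for sensitivity and specificity, by segment, at the group sizes actually to be enrolled. The limits 77.2% to 97.0% should not appear as the expected sensitivity interval for N = 280.

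When printing limits by segment, note that at 90% a segment with fewer than 44 cases would also exceed the 20-point total width (step 1).

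The cost is a few sentences in three places and a slightly less favourable statement of precision. No extra patients are needed. Only if the sponsor does intend a limit of 10 points on each side would the study need re-sizing, with specificity governing at about 344 to 348 under 75% prevalence.

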8.6 Measures to Minimize Bias

Blinding

Examiners performing the red reflex test will be blinded to all subjects and results until all study data have been collected.

Breaking the Study Blind

Breaking the study blind for red reflex performers will be at the conclusion of the study data collection period. Intentional and unintentional breaking of the blind should be reported to the PI.

Section 9: Data Quality and Oversight

9.1 Study Team Quality Assurance and Quality Control

Study data will be historical in nature, and therefore will be accurate to the patient's current diagnosis. All further evaluation will be reported by the red reflex examiner and this original data will be used in the analysis. Protocol deviations will be reported immediately or witnessed in person by the PI/co-investigator/study coordinator. Documents to be reviewed include clinic notes. The PI/co-investigator/study coordinator are responsible for reviewing the data each time the red reflex test is performed. The PI/co-investigator/study coordinator is responsible for addressing data quality issues.

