2.3 Potential Risks

There is minimal immediate or long-term risk in this study. The interventions used are included in a standard ophthalmologic exam. Patient's may experience mild discomfort from the light of the equipment (direct ophthalmoscope) shone into their eyes. Additionally, patients have a risk in breach of confidentiality from usage of PHI data. However, all steps in accordance with CNHS policy will be performed in order to ensure patient confidentiality. These minimal risks are worth the potential benefit of understanding how to perform ophthalmologic screening in the pediatric medical home.

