5.1 Study Population, Recruitment and Retention

Pediatric patients will be recruited through clinical practice at the designated study sites. Participants with known anterior segment or posterior segment pathology will be eligible for inclusion. Patients who have a history of disease, treatments and/or surgical procedures affecting the ability for normal pupillary reaction are excluded. An equal number of age matched participants with a normal anterior and posterior segment exam will be recruited from routine outpatient clinic visits. Informed consent will be obtained and will include an option to be considered for medical photography. Participants may opt out of photography and still be included in the study. For Spanish speaking participants, a telephone interpreter will be used for study recruitment and informed consent. A Spanish informed consent (developed by a Spanish medical translator from our English written consent) will be provided. Current estimated number of subjects required for the study is 200 total including 100 controls. Patient charts will be accessed from date of birth to patient's current age using either Cerner or Epic depending on the study site location. Examiners will include ophthalmology residents with one completed year of ophthalmology training. They will be blinded to participants' ophthalmologic history.

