5.2 Inclusion Criteria

There is no difference in criteria for screening and enrollment. Patients with general eyelid pathology, ptosis, corneal pathology, astigmatism, cataract, vitreous pathology, vitreous detachment, vitreous hemorrhage, retinal pathology, retinopathy of prematurity, retinal detachment, retinal tear, retinal hemorrhage, retinoblastoma, other intraocular tumors overlying or outside of the central visual axis, retinal pigmented epithelial cell pathology, choroidal pathology, optic nerve pathology, retinal artery or vein pathology may be included.

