6.4 Description of Study Procedures/Evaluations

- *Medical history—ocular history from prenatal care and on will be obtained through the medical record or in person.*
- *Medication history—Current medications taken required.*
- *Physical examinations—Subject's red reflex and pupillary size will be examined using a direct ophthalmoscope in bright and dim room lighting conditions as well as before and after pharmacologic dilation. Automated vision screening using the Spot photoscreener will be performed before and after dilation.*
- *The results of the red reflex exam will be discussed with the patient during the clinic visit.*
- *Photographs of the subject's red reflex may be taken and edited to ensure anonymity. These photographs will allow for digital analysis of the patients red reflex. These photographs will be kept on password*

protected computers at Children's National Health System and on password protected encrypted flash drives. These photographs may be used for dissemination of study results such as in conference abstracts and medical journals. Once the study is complete, original photographs may be destroyed.

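### No same-visit reference status is specified: case and control status rests on historical records, so treated or resolved disease may be misclassified and bias accuracy by an unknown amount

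*Combined protocol and SAP*

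**What the plan says.** Section 9.1 is the only place that addresses how accurate the diagnosis data are: "Study data will be historical in nature, and therefore will be accurate to the patient's current diagnosis". It continues: "All further evaluation will be reported by the red reflex examiner and this original data will be used in the analysis". The red reflex examiner performs the index test, so that evaluation cannot also be the reference. The same section adds that "Documents to be reviewed include clinic notes", without saying which visit's notes or which findings.

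The other relevant text is as follows.

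- **Cases.** Section 5.1: "Participants with known anterior segment or posterior segment pathology will be eligible for inclusion". The section does not require the pathology to be present on the study day. It also says "Patient charts will be accessed from date of birth to patient's current age". Section 6.4 says "ocular history from prenatal care and on will be obtained through the medical record or in person".
- **Eligible conditions.** The list in Section 5.2 includes cataract, vitreous hemorrhage and "retinopathy of prematurity, retinal detachment, retinal tear, retinal hemorrhage, retinoblastoma". Section 5.3 removes past disease or treatment only where it impairs normal pupillary reaction.
- **Controls.** Section 5.1 asks for a normal exam of both segments and recruits from routine clinic visits. It gives no date, method or examiner.
- **Screening.** Section 6.2 lists consent, eligibility confirmation, history and demographics between Day -30 and the visit. It lists no eye exam.
- **Dilation and photography.** Dilation is specified so that the RRT (Protocol Summary, Section 6.3) and the photoscreener (Section 6.4) can be repeated. Photography is optional, and families may decline it.
- **Analysis.** Sections 3.3 and 3.4 count eyes. Section 8.4 builds contingency tables without saying what places an eye in the diseased or the healthy margin.

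**The concern.** Sensitivity and specificity are defined against the true state of the eye when the index test is performed. A charted diagnosis shows that disease was present at some time; it does not show that disease is present now. Several of the listed conditions can regress or be treated while the pupil still reacts normally, so the exclusion criterion does not remove them.

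If such an eye is labelled diseased and its RRT is correctly read as normal, it enters the table as a false negative. If a control has developed disease since its last normal exam and the RRT correctly picks it up, it enters as a false positive. Both primary quantities are exposed, and a larger sample does not help because this is bias and not imprecision. Nor can it be repaired afterwards if status at the visit was never recorded.

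Both earlier studies described in Section 2.1 set the RRT against retinal imaging under dilation. A reference drawn from charts would make this study's estimates harder to compare with theirs.

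**Working it through.** **1. The plan's own figures.** Section 8.5 gives 59 patients for sensitivity and 280 for specificity, assuming 75% prevalence, 90% sensitivity, 80% specificity and 95% limits of ±10 points. Exact (Clopper-Pearson) intervals with a total width of at most 0.20 need 44 diseased and 70 healthy patients. Then 44 / 0.75 = 58.7, so 59, and 70 / 0.25 = 280. Both figures reproduce. The present point does not touch that arithmetic, but ±10 points is a useful yardstick for the bias.

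**2. Sensitivity.** Let f be the share of eyes labelled as cases that have no current pathology. The documents do not give f; 5% to 20% is assumed. Suppose these eyes test positive as often as healthy eyes do:

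observed Se = (1 − f) × Se + f × (1 − Sp), so bias = −f × (Se + Sp − 1).

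At the planning values and f = 10%: 0.90 × 0.90 + 0.10 × 0.20 = 0.83.

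| True Se | Sp | f = 5% | f = 10% | f = 20% |
|---|---|---|---|---|
| 90% (8.5) | 80% (8.5) | 86.5% | 83.0% | 76.0% |
| 99.6% (2.1, anterior) | 80% | 95.6% | 91.6% | 83.7% |
| 4.1% (2.1, posterior) | 80% | 4.9% | 5.7% | 7.3% |
| 4.1% | 95% (assumed) | 4.1% | 4.2% | 4.3% |
| 4.1% | 100% (assumed) | 3.9% | 3.7% | 3.3% |

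At 90%/80% the bias is −0.70 × f, which is 7 points for each 10% of case eyes. It exceeds 10 points once f is above 0.10 / 0.70 = 14.3%. Misclassification pulls sensitivity toward 1 − Sp. The shift is therefore clearly downward where true sensitivity is high, and small in either direction where it is near 4%.

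**3. Specificity.** Let g be the share of controls with undetected disease (not given; 2% to 5% assumed):

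observed Sp = (1 − g) × Sp + g × (1 − Se).

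- Se 90%, g = 2%: 0.98 × 0.80 + 0.02 × 0.10 = 78.6%.
- Se 90%, g = 5%: 0.95 × 0.80 + 0.05 × 0.10 = 76.5%.
- Se 4.1%, g = 5%: 0.95 × 0.80 + 0.05 × 0.959 = 80.8%.

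Here too the direction depends on how well the RRT detects the disease in question.

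**The case against.** The strongest reply is that the plan leaves less room for stale status than Section 9.1 alone suggests. That section speaks of the current diagnosis, and nowhere do the documents say that resolved disease is to be scored as disease. The chart-access range in Section 5.1 appears in recruitment text and does not define a case. Eligibility is confirmed within 30 days of the visit. Controls need a normal exam and come from routine visits, photography may document pathology, and the study team reviews the data each time the RRT is performed. Many conditions in Section 5.2, such as ptosis, astigmatism or optic nerve pathology, would usually persist. A treated eye with residual change may still give an abnormal reflex, so it would not be a miss.

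All of this stands as a reason to call the misclassification possible and not established. None of it fixes reference status at the visit: currency is asserted but not verified, eligibility confirmation includes no eye exam, and photography is optional.

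A second objection concerns direction. A reader might infer that misclassification could by itself create the poor posterior performance that the study hypothesises. The documents do not support this. The 90% in Section 8.5 is a planning value for anterior and posterior pathology combined. At the cited posterior value of 4.1% the effect is about three points or less up to f = 20%, and it is upward at 80% specificity. That upward case does imply a test that is positive less often in diseased than in healthy eyes. If true posterior sensitivity were moderate, the bias would run toward the hypothesis, but no such value is given.

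**Conclusion.** The point holds as a gap in the reference standard. Section 9.1 rests disease status on historical data through an inference that does not follow, and nothing else in the plan supplies per-eye, per-segment status at the time of the RRT. Regressed or treated disease may be analysed as a case, and an outdated normal exam may leave a control misclassified.

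It would go too far to say that treated or resolved disease will count as missed. That requires such eyes to be enrolled, labelled diseased and read as normal, and the documents do not show how often this would happen.

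The size of the bias cannot be estimated from the documents. The 7 points of sensitivity per 10% of case eyes rests on assumed values of f, the plan's 90%/80%, and resolved eyes behaving like healthy ones. It is relevant mainly to anterior pathology, where the cited sensitivity is high. The specificity shifts have no general direction. The plan should be changed because the correction is cheap and cannot be made after data collection.

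**What to change.** In Section 9.1, delete the inference that historical data are accurate to the current diagnosis. In Sections 9.1 and 8.4:

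- Define the reference status of each eye and each segment as the anterior segment and dilated fundus findings in that visit's clinic note. Count an eye as a case only if pathology is present at that exam, and apply the same definition to controls.
- State in advance how eyes with treated or resolved disease are handled in the tables.
- If no same-visit exam was done, use the latest exam within a fixed, pre-specified window, and repeat the analysis without those eyes.
- Record the findings before the RRT result is seen where existing staffing allows; otherwise record whether the clinician knew the result. Strict masking should not be required. The principal investigator attends the RRT (Section 6.5), results are discussed at the visit (Section 6.4) and data are reviewed each time (Section 9.1), so it could demand another examiner.

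**Cost.** Wording, plus one CRF field per eye and segment. The children are already dilated in an ophthalmology clinic and clinic notes are already reviewed. Section 2.3 also says "The interventions used are included in a standard ophthalmologic exam", although that is a statement about risk and does not guarantee a full exam that day, hence the fallback window. Some chart-diagnosed children would leave the case group, which slightly reduces precision for sensitivity. To keep the 44 confirmed diseased patients behind the plan's figure of 59, 44 / 0.90 = 48.9, so 49, would be recruited as cases at an assumed f of 10%, and 44 / 0.80 = 55 at 20%.
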